7.3.3 Unblinding

This is a double-blind study. Treatment assignments should be maintained as blinded unless such unblinding is considered as critical to the care and well-being of the subject. Unblinding should occur following discussion with the Sponsor Medical Monitor, however, emergency unblinding can occur if the Investigator deems that such a delay would unduly harm the subject and knowledge of the treatment assignment is a critical factor in medical decision making versus a discontinuation of study drug until discussion with the Medical Monitor. In the case of unblinding, the Investigator must record the date, time and reason for unblinding, however, the Investigator is not required to inform the Sponsor of treatment assignment. Unblinded treatment assignment will only be accessible to those who require such information as part of medical decision making and for those involved in Safety reporting to Health Authorities and/or the relevant IRB.

The Investigational Pharmacy will maintain a listing of subject treatment assignments and will provide a mechanism for unblinding in emergency situations.

8. STATISTICAL METHODS and CONSIDERATIONS

Prior to unblinding and analysis of the final study data, a detailed Statistical Analysis Plan (SAP) will be written describing all analyses that will be performed for reporting of results from this clinical trial.

8.1 Data Sets to be Analyzed

- The intention to treat population (ITT) includes all participants who are randomized to a treatment allocation. The ITT population will be used for the summary of all demographic and baseline characteristics and for analysis of the primary outcome of treatment failure. Subjects will be grouped in analyses and summaries based on their randomization allocation.
- The modified intention to treatment (mITT) population includes all participants who are randomized to a treatment allocation, and who have received at least one dose of study drug. The mITT population will be used for the summary and analysis of the primary outcome of treatment failure. Participants will be grouped based on the treatment allocation.
- The safety analysis set includes all mITT participants. Participants will be grouped based on the treatment actually received.
- Per-protocol (PP) analysis set includes all Safety subjects who complete the trial by meeting the endpoint or being discharged within 28-days without meeting the endpoint. Participants in this set will be grouped to treatment arms they actually received. This set will be used as a sensitivity analysis to summarize the primary endpoint and for summary of all other efficacy outcomes.

8.2 Sample Size

Based on the initial data obtained to date and data in the literature ^[1], it is anticipated that approximately 50% of subjects hospitalized with PCR-positive SARS-CoV-2 infections

(WHO COVID-19 Classification level 3 or 4) will progress to WHO COVID-19 classification level of 6 or greater as defined by one or more of the following: the need for intubation or mechanical ventilation (level 6), the need for ECMO (level 7), or any cause death (level 8). The sample size estimate for this proof of concept is based on Fisher's Exact two-sided test for 2 proportions using NQuery 8 (www.statsols.com). Estimates of admitted patients requiring salvage therapy is unknown, however, the clinical data set who require intubation is a likely subset of those whose condition worsens but do not progress to respiratory compromise.

Although the interim analysis will utilize masked treatment assignments, the O'Brien Fleming group sequential sample size estimation confirms that a single interim look would retain a cumulative exit probability of 70% with a cumulative alpha =0.05 after the final analysis using the target enrollment of 132 (44 per group) to detect a reduction of those reaching the endpoint of treatment failure, which includes advancing to WHO COVID-19 Classification level \geq 6 from 50% (SOC treated) to 25% in either treatment group of SOC plus GLS-1027. Other conditions also qualify a subject as treatment failure include: need for salvage therapy with IL-6 monoclonal antibody; or institution of salvage therapy with dexamethasone (\geq 6 mg/day), withdrawing consent from the study, becoming lost to follow-up, or discontinuation of treatment for any reason other than renal function or pregnancy. This study is not powered to assess statistically significant differences between GLS-1027 doses.

8.3 Randomization

Randomization to treatments will occurred using a centralized randomization system. Randomization will be stratified by site to ensure equal distribution of treatments within each site. Subjects within each site will be randomly assigned in a 1:1:1 ratio to receive placebo, 120 mg GLS1027 or 360 mg GLS1027 daily for their duration of hospitalization or until intubation or mechanical ventilation constrains oral medication.

8.4 Demographic and Other Baseline Characteristics

Demographic and baseline data, vital signs, medical history, concomitant illnesses, and current medications/treatments will be summarized by means of descriptive statistics: continuous variables as mean, median, standard deviation, minimum and maximum values and categorical variables as frequencies and percentages, grouped by treatment arm based on the ITT population and overall.

8.5 Safety Analysis

All safety and tolerability summaries will be performed on the safety analysis population.

8.5.1 Adverse events

Treatment emergent AEs will be summarized by frequencies and will be presented by system organ class and preferred term with the number and percentage of participants affected. Frequencies will be presented with respect to maximum severity. Multiple occurrences of the same AE will be counted only once following a worst-case approach with respect to severity and relationship to Study Treatment.

8.5.2 Laboratory Data

Continuous response variables per time point will be summarized with mean, median, minimum, and maximum values. Categorical response variables will be summarized per

time point with percentages. In addition, each laboratory parameter will be summarized as a shift from baseline based to the last lab assessments prior to meeting the primary endpoint or 28 days, whichever comes last.

8.6 Efficacy Analysis

The primary endpoint is treatment failure which is defined as any subject who achieved WHO level \ge 6 (intubation and mechanical ventilation, requirement for ECMO, or death) within 28 days of initiating treatment or who meet the following reasons for treatment failure:

- Receiving salvage therapy with either an IL-6 monoclonal antibody or for those who are prescribed daily dexamethasone starting 72 hours or later after the 1st dose of study drug within the 28-day primary treatment period.
- Lost to follow-up through hospital transfer, within the 28-day primary treatment period.
- Discontinuation of study drug for any cause prior to discharge will be considered as a treatment failure, except for those for whom study drug was suspended due to a decrease in renal function (creatinine clearance of < 60 mL/min), and those become pregnant during treatment. These subjects will be followed for the primary endpoint for up to 28 days post enrollment, and for up to 56 days for safety.

Subjects who complete 28 days of treatment but remain hospitalized without increase in WHO COVID-19 Classification level to ≥ 6 , will not considered be as treatment failures with respect to the primary endpoint.

The proportion of subjects in each treatment group who reach the study endpoint of treatment failure by 28 days will be compared to placebo using Fisher's Exact 2-sided test of proportions. Additionally, the frequency for each outcome (intubation, ECMO, death) will be determined within each group. The ITT, mITT and PP analysis populations will be used to analyze the primary endpoint.

8.7 Other Analysis

Exploratory endpoints include the following which will be summarized using the PP populations by treatment group received:

- Assess the number of days requiring ICU care relative to treatment group. If a subject does not require ICU care, the number of days will be set to zero for the group summary. The number of ICU days will be summarized for all subjects in each group and for the proportion of those who are actually in ICU.
- Assess the number of days of mechanical ventilation relative to treatment group. If a subject does not require mechanical ventilation, the number of days will be set to zero for the group summary. The number of mechanical ventilation days will be summarized for all subjects in each group and for the proportion of those who are actually on mechanical ventilation.

- Assess incidence of WHO COVID-19 Classification levels relative to baseline serum IL-6 level
- Assess incidence of WHO COVID-19 Classification levels relative to baseline serum ferritin level
- Assess incidence of WHO COVID-19 Classification levels relative to baseline CRP
- Assess trough level of GLS-1027 relative to serum creatinine
- Assess the maximal level of Positive End-Expiratory Pressure (PEEP) for subjects who are intubated relative to treatment group.
- Assess the number of days of PEEP > 5 cm H₂O for subjects who are intubated relative to treatment group
- Incidence of progression to WHO COVID-19 Classification level 6, or 7, or 8 (individually)
- Assess SARS-CoV-2 IgM antibody responses relative to treatment group

No adjustments or imputations will be made for deaths or other forms of missingness except those already described above.

8.8 Interim Analysis

A masked interim analysis will be performed when 22 subjects in each group have been assessed for the primary endpoint of treatment failure. Unless safety is of concern, the study will not be stopped for futility and enrollment will continue to at least the targeted sample size of 132.

8.9 Missing Values

Subjects may have a missing endpoint for the following reasons:

- Lost to follow up due to transfer to another hospital
- Remains in the hospital for >28 days without ever achieving WHO COVID-19 Classification level ≥ 6.
- Withdrawal of consent prior to meeting endpoint

If a subject is lost to follow-up due to transfer to another hospital, the subject will be considered a treatment failure per the ITT and mITT populations and will be excluded from the analysis per the PP population. Missing primary endpoint assessment because of continued hospitalization beyond 28 days will be counted as treatment success if the subject has not met the criteria for WHO COVID-19 Classification level \geq 6 at any time up to 28 days. Subject who withdraw consent without being assessed for the primary endpoint will be considered treatment failure. To minimize missing values, enrolled participants will be followed through to the end of the primary study period (through to hospital discharge, death, or 28 days from treatment initiation) for safety and efficacy assessment. Additionally, safety and clinical status will be monitored through to Day 56 as per the schedule of events.

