3.2 Data and Safety Monitoring Board (DSMB)

In addition to internal monitoring of safety data by the site PI and medical monitor, an independent data and safety monitoring board (DSMB), consisting of expert members not related to the clinical trial or sponsor staff will provide safety oversight. The DSMB will include at a minimum three members: a physician specializing in either Infectious Disease or Pulmonary / Critical Care, a second health-care practitioner who may be a physician, and someone with statistical experience (physician or non-physician).

The DSMB will meet at the start of the clinical trial to review and finalize the DSMB charter. At a minimum, the DSMB will meet to review interim data when 50% of the target enrollees (66 subjects) have completed the primary observation period to discharge, death, discontinuation or 28 days of treatment. The DSMB will review safety data and outcomes for enrolled subjects in a blinded manner. Unless a safety signal has been encountered, enrollment will continue through to at least 44 per group (total N=132).

A summary of all AEs and SAEs will be provided to the DSMB as masked treatment groups by an independent statistician together with a summary rates of retention in the study, and other relevant events. Reports will include a summary of participants' baseline characteristics, early study discontinuations, and a summary of participants who reach primary endpoint and/or end of study follow-up. The DSMB may recommend corrective measures, up to termination of the study for safety concerns. Study termination can be implemented by the Project PI, FDA, Sponsor, or site-specific or other supervising IRBs. Conference call or video conference meetings are allowed as necessary.

Additional details can be found in the DSMB Charter.

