4.4 Discontinuation/Withdrawal of Study Participants

The Informed Consent will require that subjects allow follow-up for the primary outcome and safety through to 56 days post-enrollment or death. A subject may withdraw from the study by withdrawing consent to continue participation. If a subject withdraws consent from participating in the study at any time after enrollment, but prior to the final scheduled study visit, the investigator will make every effort to have the participant complete all assessments at the time of withdrawal. All data collected up to the time of withdrawal will be used for data analyses. The request to withdraw consent must be documented.

Discontinuing treatment is not a reason for withdrawing from participating in the study. Subjects who discontinue treatment for any reason should be followed until 56 days postenrollment or death, whichever comes first.

Reasons for treatment discontinuation are defined below.

- The PI or Medical Monitor consider that continuation of treatment may pose a safety risk to the subject. Treatment discontinuation will be considered a treatment failure, unless the subject discontinues treatment due to pregnancy or renal insufficiency. The subject should however continue to be monitored as per protocol for outcome measures through to study end (Day 56).
- Adverse event (Adverse Reaction): clinical or laboratory events that in the medical judgement of the investigator are grounds for discontinuation of treatment. This will be considered as a treatment failure. Subjects should however continue to be monitored as per protocol for outcome measures through to study end (Day 56).
- Lost to follow-up: for subjects who are discharged from the hospital within 28 days of treatment initiation who cannot be contacted after multiple attempts, will be

considered as Lost to Follow-up for purposes of Long-term outcomes (56 days). Otherwise, without relapse of COVID-19 symptoms, discharge within 28 days of enrollment is considered a treatment success. For subjects who are discharged from the hospital, every effort should be made to contact the subject to determine clinical status and adverse events post-discharge.

• Transfer of subject to another hospital. All transfers will be considered treatment failures.

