- ¹ PK assessment will be performed for the initial 15 subjects enrolled. Blood (5 ml) will be collected for plasma collection at baseline (pre-treatment), and then at 1, 2, 4, and 8 hr. Trough measurements will be obtained as indicated for all study participants
- ^m The clinical record should be reviewed at Day 28 and Day 56 as relevant to denote date of discharge, date of death, or clinical status (WHO COVID-19 Classification Level); if discharged, subjects should be contacted by telephone to ascertain clinical status.
- ⁿ PBMCs will be collected at specified sites only

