8.3. Definition of the Exploratory Efficacy Endpoints

Exploratory endpoints include the following which will be summarized using the PP populations by treatment group received:

- Assess the number of days of hospitalization relative to treatment group
- Assess the number of days requiring ICU care relative to treatment group. If a subject does not require ICU care, the number of days will be set to zero for the group summary. The number of ICU days will be summarized for all subjects in each group and for the proportion of those who are actually in ICU.
- Assess the number of days of non-invasive or mechanical ventilation relative to treatment group. If a subject does not require non-invasive or mechanical ventilation, the number of days will be set to zero for the group summary. The number of mechanical ventilation

CONFIDENTIAL Page 11 03DEC2021

days will be summarized for all subjects in each group and for the proportion of those who are actually on mechanical ventilation.

- Assess incidence of WHO COVID-19 Classification levels relative to baseline serum IL-6 level
- Assess incidence of WHO COVID-19 Classification levels relative to baseline serum ferritin level
- Assess incidence of WHO COVID-19 Classification levels relative to baseline CRP
- Assess trough level of GLS-1027 relative to serum creatinine
- Assess the maximal level of Positive End-Expiratory Pressure (PEEP) for subjects who are intubated relative to treatment group.
- Assess the number of days of PEEP > 5 cm H2O for subjects who are intubated relative to treatment group
- Assessment of WHO COVID-19 Classification at 28 day relative to treatment group
- Assess SARS-CoV-2 IgM antibody responses relative to treatment group

No adjustments or imputations will be made for deaths or other forms of missingness except those already described above.

Corticosteroids will be recorded as a prior or concomitant medication. Subgroup analysis will be performed to compare outcomes relative to treatment group and relative to use or non-use of corticosteroids. Primary treatment outcomes will be determined from the time of enrollment through to Day 28.

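### The protocol contradicts itself on whether intubation or death between discharge and Day 28 counts as a primary-endpoint failure

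*Protocol*

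**What the plan says.** Some passages close the efficacy window at discharge:

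- Protocol 8.9 follows participants to the end of the "primary study period (through to hospital discharge, death, or 28 days from treatment initiation) for safety and efficacy assessment".
- Protocol 3.2 times the interim safety review by patients who "have completed the primary observation period to discharge, death, discontinuation or 28 days of treatment".
- Protocol 6.1.3 records WHO level daily on Days 2 to 29 but stops at discharge or death. The next listed visit is Day 56.
- Protocol 4.4 states that, "without relapse of COVID-19 symptoms, discharge within 28 days of enrollment is considered a treatment success".

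Others run it to Day 28 or beyond:

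- Protocol 2.2 and 8.6 define treatment failure over 28 days and do not mention discharge as a stopping point. Level 6 or above includes death, and Protocol 8.2 specifies death from any cause.
- Protocol 4.4 also has the consent form require that "subjects allow follow-up for the primary outcome and safety through to 56 days post-enrollment or death". Footnote m of Table S2 has the record reviewed to Day 56 for discharge date, death date or clinical status.
- SAP 8.1 sets the endpoint at 28 days from enrollment, and SAP 8.3 adds: "Primary treatment outcomes will be determined from the time of enrollment through to Day 28".
- SAP Table 1, footnote m, calls for a record review at Day 28 and Day 56; "if discharged, subjects should be contacted by telephone to ascertain clinical status".

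**The concern.** Section 4.4 is the only text that assigns an outcome to a discharged patient, and for some patients that outcome is the opposite of the one 8.6 gives. The programmer who derives the primary endpoint would have to choose between the two without guidance.

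Ascertainment raises a second issue. If post-discharge events count, they have to be found. The protocol has no Day 28 contact for discharged patients. The SAP adds one, but it records discharge date, death date or clinical status. It does not ask for the worst level reached since discharge.

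At stake is a handful of patients in a comparison of 44 v 44, where one reclassified patient can matter.

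**Working it through.** **Step 1. Score three patients under each passage.** Each is discharged on Day 6 without having failed.

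| Course after discharge | Protocol 4.4 | Protocol 8.6 | SAP 8.1 / 8.3 |
|---|---|---|---|
| Dies on Day 20, no COVID-19 relapse | Success | Failure | Failure |
| Intubated on Day 15 for another reason, no relapse | Success | Failure | Failure |
| COVID-19 relapse, readmitted and intubated on Day 15 | Not made a success (relapse condition) | Failure | Failure |

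The contradiction is confined to the first two rows. It lies inside the protocol, between 4.4 and 8.6, and the SAP agrees with 8.6.

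**Step 2. Check whether the event would be found.** A death is dated by record review under either document. If the second patient is intubated at another hospital and has recovered by Day 28, clinical status that day need not reveal the event, although SAP 8.1 counts it.

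**Step 3. Reproduce the plan's power.** Inputs from Protocol 8.2: 50% v 25%, 44 per group, two-sided alpha 0.05, one O'Brien-Fleming look, stated power 70%.

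- Standardised difference, unpooled: 0.25 / √[(0.50×0.50 + 0.25×0.75)/44] = 0.25 / 0.0997 = 2.507.
- Fixed-sample power: Φ(2.507 − 1.960) = 70.8%.
- With two looks at half and full information (critical values 2.963 and 1.969), power is 70.6%, so the stated 70% reproduces.
- Exact two-sided Fisher, the test named for the analysis, gives 61.1% by enumeration. It is the reference below.

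**Step 4. Add post-discharge failures.** The documents give no rate, so these are assumptions. Take 50% and 25% as the rates before discharge, treat all remaining patients as discharged, and let shares qP (placebo) and qA (active) of them fail by Day 28.

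- Placebo rate = 0.50 + 0.50×qP
- Active rate = 0.25 + 0.75×qA
- Difference = 0.25 + 0.50×qP − 0.75×qA
- Patients who change status per 44: placebo 44×0.50×qP; active 44×0.75×qA

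| qP / qA (assumed) | Rates | Difference | Status changes, placebo / active | Fisher power |
|---|---|---|---|---|
| 0 / 0 | 50.0% v 25.0% | 25.0 points | 0 / 0 | 61.1% |
| 2% / 2% | 51.0% v 26.5% | 24.5 | 0.44 / 0.66 | 58.2% |
| 4% / 4% | 52.0% v 28.0% | 24.0 | 0.88 / 1.32 | 55.3% |
| 6% / 6% | 53.0% v 29.5% | 23.5 | 1.32 / 1.98 | 52.4% |
| 6% / 3% | 53.0% v 27.25% | 25.75 | 1.32 / 0.99 | 62.0% |

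**Step 5. Direction.** Counting these events shrinks the difference only if 0.75×qA > 0.50×qP, that is, if qA exceeds two-thirds of qP. Equal rates meet that condition; a halved active rate does not.

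**Step 6. Sensitivity to one patient.** 22/44 v 12/44 gives Fisher p = 0.048, and 22/44 v 13/44 gives p = 0.081. This boundary case was chosen to show sensitivity. It is not a forecast.

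**The case against.** The strongest reply is that the endpoint is already clear. Protocol 8.6 defines it, 2.2 and the SAP agree, and neither 8.9 nor 3.2 is a scoring rule: the first is about limiting missing data, and the second times a safety review. Protocol 8.9 itself goes on to have safety and clinical status monitored to Day 56. Protocol 4.4 asks for every effort to contact discharged patients, and deaths and hospitalisations are reportable as serious adverse events.

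Most of this stands. It disposes of a reading that a reader might infer, namely that the protocol stops the endpoint at discharge while the SAP runs it to Day 28. The protocol's own endpoint runs to 28 days. Nor does 4.4 turn a patient readmitted and intubated for COVID-19 into a success, because its rule is conditional on no relapse.

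A reader might also infer that stopping at discharge overstates the drug's benefit. That needs an assumption about post-discharge risk that the documents do not supply, and Step 5 shows that the direction can reverse.

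Finally, the SAP cites protocol version 5.0, describes 14 days of treatment, and counts high-flow oxygen or non-invasive ventilation as failure. The protocol supplied has 28 days of treatment and no such component. Part of the mismatch with the SAP may therefore be between versions, which the documents do not settle.

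What survives is the explicit success rule in 4.4. It contradicts 8.6 within the same protocol, so a version difference from the SAP does not explain it. The ascertainment gap also survives.

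**Conclusion.** The concern holds as an internal contradiction in the protocol. Section 4.4 makes a success of a patient discharged without relapse who dies, or is intubated for another reason, before Day 28; section 8.6 and the SAP make the same patient a failure. Sections 3.2, 6.1.3 and 8.9 add to the uncertainty by ending efficacy observation at discharge, but they do not score events. The SAP's Day 28 contact reduces the ascertainment gap without closing it.

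Neither the size nor the direction of the effect is known. Under the assumed rates the treatment difference moves by −1.5 to +0.75 points and Fisher power lies between 52.4% and 62.0%, against 61.1% with no post-discharge events. These figures rest on treating the planning rates as pre-discharge rates and on invented post-discharge rates, so they illustrate scale only. The effect is modest on average but could decide a result near the 0.05 boundary.

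**What to change.** Align Protocol 3.2, 4.4, 6.1.3 and 8.9 with Protocol 8.6 and SAP 8.1 in one statement: WHO level 6 or above, or death, through Day 28 is a treatment failure whether or not the patient has been discharged. Amend the success sentence in 4.4 to require no such event by Day 28.

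Have the existing Day 28 record review and telephone call capture any readmission, the highest respiratory support since discharge, and the dates. Put that contact in the protocol as well as the SAP.

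The same statement should say how a discharged patient who cannot be reached at Day 28 is scored. Protocol 4.4 treats such a patient as lost for the 56-day outcome only, whereas the shell for SAP Table 14.2.1.1 lists loss to follow-up and a missing WHO assessment among the reasons for failure.

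Confirm which protocol version governs before editing. The cost is wording in two documents, a few form fields, and possibly slightly higher failure rates.
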